4.1. Objectives and Endpoints

Table GPGO.1 shows the objectives and endpoints of Study GPGO protocol addendum, which are in addition to the Study GPGO protocol body.

Table GPGO.1. Objectives and Endpoints

Objectives	Endpoints

Pharmacokinetics
 
 To evaluate the pharmacokinetic profile of once-weekly tirzepatide in Japanese patients with T2DM using the commercial formulation 	
 AUC and C_{\max} of tirzepatide

Exploratory
 
 To compare the effect of once-weekly tirzepatide versus dulaglutide 0.75 mg on the pharmacodynamic profile and satiety after a standardized test meal at Week 32 To compare the effect of once-weekly tirzepatide versus dulaglutide 0.75 mg on daily glucose variability measured by CGM at Week 32 To compare the effect of once-weekly tirzepatide versus dulaglutide 0.75 mg on body composition at Week 12, 32, and 52 	
 The change from baseline in serum glucose $AUC_{(0-6h)}$ The change from baseline in insulin $AUC_{(0-6h)}$ The change from baseline in C-peptide $AUC_{(0-6h)}$ The change from baseline in glucagon $AUC_{(0-6h)}$ The change from baseline in triglyceride $AUC_{(0-6h)}$ The change from baseline in satiety (full and hungry) in VAS Daily average glucose (mg/dL) Time in range ≤ 70 mg/dL (minutes) Time in range > 180 mg/dL (minutes) Daily within-day SD (mg/dL) Daily MAGE (mg/dL) The change from baseline in total body water (L) The change from baseline in protein (kg) The change from baseline in minerals (kg) The change from baseline in body fat mass (kg) The change from baseline in lean body mass (kg)

Abbreviations: AUC = area under the concentration versus time curve; $AUC_{(0-6h)}$ = area under the concentration versus time curve from time zero to 6 hours after dose; C_{\max} = maximum concentration; CGM = continuous glucose monitoring; MAGE = mean amplitude of glycemic excursion; T2DM = type 2 diabetes mellitus; VAS = visual analog scale.

4.2. Determination of Sample Size

A total of 48 patients will be randomized in a 1:1:1:1 ratio to 1 of 4 treatments. Assuming 1 dropout, the sample size of 11 patients for each treatment group would provide 79% power to demonstrate a statistically significant difference between the tirzepatide dose levels and dulaglutide 0.75 mg. This computation assumes the true treatment difference in glucose AUC(0-6h) is 330 mg*hr/dL, a common standard deviation of 250 mg*hr/dL.

5. A Priori Statistical Methods

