4.3.2. Number of Participants

The total number of participants for this addendum is approximately 48 patients, which is based on the objectives of PK and glucodynamic effect.

To evaluate the glucodynamic effect, a total of 48 participants (12 participants per treatment) will be needed. The assumptions for this sample size are described in Section 4.5.1. To provide the PK and pharmacodynamic (PD) evaluation similar to the historical conventional Phase 1 studies, samples from approximately 10 patients in the treatment arms of tirzepatide 5 mg, 10 mg, 15 mg, and/or dulaglutide 0.75 mg will be needed.

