4.3.3. Scientific Rationale for Study Design

This addendum is designed to evaluate PK, glucodynamic, and PD effects after a standardized test meal. Patients with T2DM who have diet and exercise therapy only will be enrolled to exclude the background effect of other antidiabetic agents. A Japanese standardized test meal (480 kcal, carbohydrate: protein: fat = 2.8:1:1) was selected because it was used in the previous MTTs conducted in Japan (Lee et al. 2010; Yabe et al. 2010; Yabe et al. 2015).

Pharmacokinetic samples will be collected at Week 0 and Week 32 to enable the evaluation of the PK of tirzepatide after a single dose and at steady state for all treatment arms.

Continuous glucose monitoring will be performed on Day -7 through Day 7 at Week 0 and Week 32, and MTT will be performed at Week -1 (Day-7 of Week 0) and Week 32, which are to enable the evaluation of tirzepatide at steady state for all treatment arms.

Body composition will be measured at Weeks 0, 12, 32, and 52 to enable evaluating time course of change of body composition during the study period. The time point was determined based on the reference data in combination of luseogliflozin and liraglutide (Seino et al. 2018). In the study described in the reference, time points were 0, 4, 12, 24, and 52 weeks.

4.3.4. *Lifestyle and/or Dietary Requirements*

4.3.4.1. *Meals and Dietary Restrictions*

Study participants should be instructed to continue diet therapy during the study period. Study participants must be fasting at least 10 hours before intake of a test meal for the MTT.

4.4. *Study Assessments and Procedures*

Section 4.1 lists the Schedule of Activities, detailing the study procedures and their timing.

[Attachment 1](#) lists the laboratory tests that will be performed for the MTT.

[Attachment 2](#) provides a summary of the maximum number and volume of invasive samples, for all sampling, during the study.

[Attachment 3](#) provides a summary of MTT procedures.

4.4.1. *Pharmacokinetics*

In the historical conventional Phase 1 study, the PK of tirzepatide was evaluated in approximately 12 Japanese subjects per treatment arm with a different titration regimen from Phase 3 studies. This study intends to obtain PK data from approximately 10 patients per treatment arm; PK samples will be collected from 12 patients in each of the treatment arms of tirzepatide (5-mg, 10-mg, and 15-mg arms) and the dulaglutide 0.75-mg arm.

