4.5.2.2. Pharmacodynamic Statistical Inference

Pharmacodynamic analyses will be conducted using data from all patients who receive at least 1 dose of the investigational product and have evaluable PD.

The change in PD parameters from baseline to Week 32 will be analyzed by an analysis of covariance (ANCOVA) model with treatment, baseline BMI group (<25 or ≥ 25 kg/m²) and washout of antidiabetic medication (yes or no) and baseline value (Week -1 [Day-7 of Week 0]) of the dependent variable as a covariate. The least-squares mean (LS Mean), standard error (SE) and the 95% confidence interval (CI) derived from the model will be displayed for change from baseline by treatment group. Treatment comparisons will be displayed showing the treatment difference LS Mean and the 95% CI of treatment differences along with the p-values for the treatment comparison. Statistical tests will be conducted using 2-sided tests and a significance level of 0.05. No multiplicity adjustment will be applied.

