5.1. General Considerations

Unless otherwise noted, all tests of treatment effects will be conducted at a 2-sided alpha level of 0.05, and the confidence interval (CI) will be calculated at 95%, 2-sided. In statistical summaries and analyses, patients will be analyzed as randomized.

Exploratory efficacy parameters will be assessed using the modified intention-to-treat (mITT) population, which consists of all randomly assigned participants who are exposed to at least 1 dose of investigational product. The primary efficacy of tirzepatide versus dulaglutide 0.75 mg at 32 weeks will be guided by the “efficacy” estimand using the efficacy analysis set (EAS).

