5.2. Multiple Comparisons/Multiplicity

No multiplicity adjustments will be made for evaluating objectives in this analysis addendum.

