5.5. Meal Tolerance Test

Exploratory objective relative to meal tolerance test is to compare the effect of once-weekly 5 mg, 10 mg and 15 mg tirzepatide versus dulaglutide 0.75 mg on the pharmacodynamic (PD) profile and satiety after a standardized test meal at Week 32 for the following endpoints:

- The change from baseline in serum glucose $AUC_{(0-6h)}$
- The change from baseline in insulin $AUC_{(0-6h)}$
- The change from baseline in C-peptide $AUC_{(0-6h)}$
- The change from baseline in glucagon $AUC_{(0-6h)}$
- The change from baseline in triglyceride $AUC_{(0-6h)}$
- The change from baseline in satiety (full and hungry) in VAS

PD analyses will be conducted using data from all patients who receive at least 1 dose of the investigational product and have evaluable PD parameter. The AUCs will be calculated using the linear-trapezoidal method and actual times.

The change in PD parameters from baseline to Week 32 will be analyzed by an analysis of covariance (ANCOVA) model with treatment, baseline HbA1c group ($\leq 8.5\%$, $> 8.5\%$), baseline BMI group (< 25 or ≥ 25 kg/m²) and washout of antidiabetic medication (yes or no) and baseline value (Week -1 [Day-7 of Week 0]) of the dependent variable as a covariate. The least squares

mean (LSM), standard error (SE) and the 95% confidence interval (CI) derived from the model will be displayed for change from baseline by treatment group. Treatment comparisons will be displayed showing the treatment difference LSM and the 95% CI of treatment differences along with the p-values for the treatment comparison.

Satiety after a standardized test meal (Satiety, Hunger and Satiety/Hunger) in the VAS will be summarized by treatment and time after a standardized test meal (0 [pre-meal], 60, 120, 180, 240, 300, and 360 minutes).

A comparison of tirzepatide doses and dulaglutide 0.75 mg will be conducted by ANCOVA model with treatment, baseline HbA1c group ($\leq 8.5\%$, $> 8.5\%$), baseline BMI group (< 25 or ≥ 25 kg/m²) and washout of antidiabetic medication (yes or no) and baseline value of the dependent variable as a covariate. The LSM, SE and the 95% CI derived from the model will be displayed for change from baseline by treatment group. Treatment comparisons will be displayed showing the treatment difference LSM and the 95% CI of treatment differences along with the p-values for the treatment comparison.

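### The stated 79% power does not follow from its printed inputs: a two-sample t-test gives about 84% per dose, and the documents do not name the method used

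*SAP*

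**What the plan says.** Protocol Section 4.5.1 and SAP Section 4.2 carry the same sample-size statement. It randomizes 48 patients equally to four treatments, allows for one dropout, and concludes that "the sample size of 11 patients for each treatment group would provide 79% power to demonstrate a statistically significant difference". The effect assumptions follow: "This computation assumes the true treatment difference in glucose AUC(0-6h) is 330 mg*hr/dL, a common standard deviation of 250 mg*hr/dL". Protocol Section 4.3.2 relies on this calculation: "To evaluate the glucodynamic effect, a total of 48 participants (12 participants per treatment) will be needed", and it refers the reader to Section 4.5.1 for the assumptions.

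The significance level is not in the sample-size sections, but it is fixed elsewhere. The Protocol's section on pharmacodynamic inference says "Statistical tests will be conducted using 2-sided tests and a significance level of 0.05. No multiplicity adjustment will be applied". SAP Section 5.1 says "all tests of treatment effects will be conducted at a 2-sided alpha level of 0.05", and SAP Section 5.2 says "No multiplicity adjustments will be made for evaluating objectives in this analysis addendum".

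The planned analysis of the endpoint is in SAP Section 5.5: "The change in PD parameters from baseline to Week 32 will be analyzed by an analysis of covariance (ANCOVA) model with treatment". That model also has three stratification factors and the baseline value. The Protocol's version has two of those factors and the baseline value.

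**The concern.** A reader has everything needed for a standard power calculation: 11 per group, a difference of 330, an SD of 250, two-sided 0.05 and no adjustment. Those inputs should return the printed 79%, and they do not.

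The sentence also leaves three things open. It names no test. It does not say whether 250 is the SD of the AUC, of its change from baseline (the actual endpoint), or of the model residual. It refers to the dose levels collectively, so it is unclear whether the power is for each dose or for all three together.

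What is at stake is the accuracy of a reported figure that appears in two controlled documents and may be carried into later reports. The size of the addendum is not at stake.

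**Working it through.** **Inputs.** Evaluable patients per group n = 11, reading the one dropout as one per group (12 − 1); difference 330 and SD 250 (SAP 4.2, Protocol 4.5.1); two-sided α = 0.05 (SAP 5.1, Protocol pharmacodynamic inference section); no multiplicity adjustment (SAP 5.2). The standardized difference is 330/250 = 1.32.

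**Attempt to reproduce 79%: two-sample t-test, one dose against dulaglutide.**

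- Noncentrality = 1.32 × √(11/2) = 1.32 × 2.345 = 3.096.
- Degrees of freedom = 2 × 11 − 2 = 20; critical value 2.086.
- Power from the noncentral t distribution = 83.7%. The stated 79% is 4.7 points lower.

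**Other calculations on the same inputs, 11 per group.**

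| Method | Power per dose |
|---|---|
| Welch t-test (simulated) | 83.3% |
| Error pooled over four arms, df = 44 − 4 = 40 | 85.6% |
| Normal approximation, Φ(3.096 − 1.960) | 87.2% |
| Four-arm ANCOVA, Protocol covariates (3), df = 37 | about 82.5% |
| Four-arm ANCOVA, SAP covariates (4), df = 36 | about 81.5% |

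The ANCOVA rows take 250 as the residual SD, which is an assumption. They allow for chance covariate imbalance by inflating the variance of the treatment contrast by 1 + p/(df − 1), where p is the number of covariates:

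- Three covariates: inflation 1 + 3/36 = 1.083; noncentrality 3.096/√1.083 = 2.974; power 82.5%.
- Four covariates: inflation 1 + 4/35 = 1.114; noncentrality 3.096/√1.114 = 2.933; power 81.4%.

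Simulation with binary strata and simple randomization gave 82.6% for three covariates and 81.5% to 81.7% for four. Stratified randomization would reduce the loss from imbalance and so move these figures further from 79%.

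**Could rounding explain it?** Suppose 330 and 250 were each rounded to the nearest 10. The t-test power then lies between 81.1% (325 with SD 255) and 86.2% (335 with SD 245), so 79% is outside the range.

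**What would give 79% by t-test at n = 11?** An SD of about 266, a difference of about 310, or α of about 0.035. None of these is in the documents.

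**Unstated variants.**

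- t-test with 10 per group: 79.7%, which would round to 80%. With 12 per group: 87.1%.
- Two-arm ANCOVA with two covariates, df = 18: inflation 1 + 2/17 = 1.118, power about 79%.
- Two-arm ANCOVA with three covariates: about 76%. With four: about 73%.
- Exact Wilcoxon test, normal data: 80.9%. Noether's formula: 75.1%.
- One-sided 0.05: 91.0%.
- Bonferroni over three doses: 68% to 72%. Dunnett: 74%.
- All three doses significant together, each with a true difference of 330: about 67% to 73%, depending on method. Reading the sentence as joint power therefore does not recover 79% either.

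**The case against.** The strongest reply is that the 79% may be undocumented and not miscalculated. The sample-size text names no test, so measuring the gap against a t-test imputes a method to the sponsor. A two-arm ANCOVA with two covariates lands on about 79%, and an exact Wilcoxon test comes within about two points. Against the planned SAP model the gap is only about 2.5 points, and that depends on treating 250 as the residual SD and on assumed covariate distributions. Printing 84% for a t-test would also leave the power statement and the planned ANCOVA on different footings.

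The reply adds that nothing depends on the figure. No estimate, interval or p-value uses it, the endpoint is exploratory, and the SAP version in hand was approved shortly before database lock.

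Most of this stands as a comment on cause and weight. The source of the 79% is unknown, and the range of 81.5% to 87% covers parametric calculations only. It does not rescue the figure. Neither document plans a two-arm model or a rank test, and the covariate counts are three and four, not two. If one of those methods was used, the plan had to say so. The remedy therefore has to allow for either a wrong number or an undisclosed method.

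**Conclusion.** The concern holds. The printed inputs give 83.7% power for each tirzepatide dose against dulaglutide by t-test, 4.7 points above the stated 79%. Across the other parametric calculations shown, including the planned ANCOVA, the gap runs from about 2.5 points (81.5%) to 8.2 points (87.2%). The t-test and normal results rest only on the documents' figures and on reading the dropout as one per group. The ANCOVA results also assume that 250 is the residual SD.

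The weight is modest. On these inputs the plan understates per-dose power, so the error is conservative. The pharmacokinetic objective separately supports the group size: Protocol Section 4.4.1 says "This study intends to obtain PK data from approximately 10 patients per treatment arm". Twelve patients per arm remains adequate on the plan's own assumptions. This is a correction to a reported number and should be made.

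**What to change.** Retrieve the calculation behind the 79%, then correct the sentence in both Protocol Section 4.5.1 and SAP Section 4.2.

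- If it was meant as a t-test on the printed inputs, restate it along these lines: *With 11 evaluable patients per group, power is about 84% for each tirzepatide dose versus dulaglutide 0.75 mg (two-sample t-test, two-sided 0.05, unadjusted, difference 330, SD 250).*
- If the figure came from another input or method, such as 10 evaluable per group or a covariate-adjusted pairwise model, print that instead, with the power it gives.
- In either case, say whether 250 is the SD of the AUC, of its change from baseline or of the model residual, and that the power is per dose.
- If the power is quoted for a t-test, add that the analysis itself is the ANCOVA of SAP Section 5.5, so that the two are not confused.

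A joint figure for all three doses is optional. The cost is one sentence in each document. The sample size, visits and analyses do not change.

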5.1. General Considerations

Unless otherwise noted, all tests of treatment effects will be conducted at a 2-sided alpha level of 0.05, and the confidence interval (CI) will be calculated at 95%, 2-sided. In statistical summaries and analyses, patients will be analyzed as randomized.

Exploratory efficacy parameters will be assessed using the modified intention-to-treat (mITT) population, which consists of all randomly assigned participants who are exposed to at least 1 dose of investigational product. The primary efficacy of tirzepatide versus dulaglutide 0.75 mg at 32 weeks will be guided by the “efficacy” estimand using the efficacy analysis set (EAS).

5.2. Multiple Comparisons/Multiplicity

No multiplicity adjustments will be made for evaluating objectives in this analysis addendum.

5.3. Patient Disposition

Listing of final study disposition and a listing of randomized treatment assignment (planned treatment) for all randomized patients in the study addendum will be provided. Summary of final study disposition and study drug disposition for all randomized patients will be provided by planned treatment.

5.4. Patient Characteristics

All demographic and baseline clinical characteristics will be summarized by study treatment for the patients in the mITT set, for those patients who participated in the protocol addendum.

5.5. Meal Tolerance Test

Exploratory objective relative to meal tolerance test is to compare the effect of once-weekly 5 mg, 10 mg and 15 mg tirzepatide versus dulaglutide 0.75 mg on the pharmacodynamic (PD) profile and satiety after a standardized test meal at Week 32 for the following endpoints:

- The change from baseline in serum glucose $AUC_{(0-6h)}$
- The change from baseline in insulin $AUC_{(0-6h)}$
- The change from baseline in C-peptide $AUC_{(0-6h)}$
- The change from baseline in glucagon $AUC_{(0-6h)}$
- The change from baseline in triglyceride $AUC_{(0-6h)}$
- The change from baseline in satiety (full and hungry) in VAS

PD analyses will be conducted using data from all patients who receive at least 1 dose of the investigational product and have evaluable PD parameter. The AUCs will be calculated using the linear-trapezoidal method and actual times.

The change in PD parameters from baseline to Week 32 will be analyzed by an analysis of covariance (ANCOVA) model with treatment, baseline HbA1c group ($\leq 8.5\%$, $> 8.5\%$), baseline BMI group (< 25 or ≥ 25 kg/m²) and washout of antidiabetic medication (yes or no) and baseline value (Week -1 [Day-7 of Week 0]) of the dependent variable as a covariate. The least squares

mean (LSM), standard error (SE) and the 95% confidence interval (CI) derived from the model will be displayed for change from baseline by treatment group. Treatment comparisons will be displayed showing the treatment difference LSM and the 95% CI of treatment differences along with the p-values for the treatment comparison.

Satiety after a standardized test meal (Satiety, Hunger and Satiety/Hunger) in the VAS will be summarized by treatment and time after a standardized test meal (0 [pre-meal], 60, 120, 180, 240, 300, and 360 minutes).

A comparison of tirzepatide doses and dulaglutide 0.75 mg will be conducted by ANCOVA model with treatment, baseline HbA1c group ($\leq 8.5\%$, $> 8.5\%$), baseline BMI group (< 25 or ≥ 25 kg/m²) and washout of antidiabetic medication (yes or no) and baseline value of the dependent variable as a covariate. The LSM, SE and the 95% CI derived from the model will be displayed for change from baseline by treatment group. Treatment comparisons will be displayed showing the treatment difference LSM and the 95% CI of treatment differences along with the p-values for the treatment comparison.

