Attachment 3. Protocol Addendum GPGO(1) Meal Tolerance Test

Meal Tolerance Test, Protocol Addendum I8F-JE-GPGO(1)

Time	Procedure
Before MTT	All evaluations for a regular visit
	Blood sampling for serum glucose, insulin, C-peptide, glucagon, and triglyceride (for 0 min)
	Satiety evaluation (VAS) (for 0 min)
	Dose of investigational product at Week 32
0 min	Start standardized test meal ^c
30 min ^a	Blood sampling for serum glucose, insulin, C-peptide, glucagon, and triglyceride
60 min ^a	Blood sampling for serum glucose, insulin, C-peptide, glucagon, and triglyceride Satiety evaluation (VAS)
90 min ^a	Blood sampling for serum glucose, insulin, C-peptide, glucagon, and triglyceride
120 min ^a	Blood sampling for serum glucose, insulin, C-peptide, glucagon, and triglyceride Satiety evaluation (VAS)
180 min ^b	Blood sampling for serum glucose, insulin, C-peptide, glucagon, and triglyceride Satiety evaluation (VAS)
240 min ^b	Blood sampling for serum glucose, insulin, C-peptide, glucagon, and triglyceride Satiety evaluation (VAS)
300 min ^b	Blood sampling for serum glucose, insulin, C-peptide, glucagon, and triglyceride Satiety evaluation (VAS)
360 min ^b	Blood sampling for serum glucose, insulin, C-peptide, glucagon, and triglyceride Satiety evaluation (VAS)

Abbreviations: min = minutes; MTT = meal tolerance test; VAS = visual analog scale.

a For each time point, ± 5 minutes for sampling window is allowed.

b For each time point, ± 10 minutes for sampling window is allowed.

c A Japanese standard test meal (480 kcal, carbohydrate: protein: fat = 2.8:1:1) should be ingested within 15 minutes.

Leo Document ID = 8d79f639-cfb0-47dc-ba71-d5571a192143

Approver: PPD

Approval Date & Time: 18-Dec-2018 02:45:37 GMT

Signature meaning: Approved

Approver: PPD

Approval Date & Time: 18-Dec-2018 09:18:48 GMT

Signature meaning: Approved

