5.6. Continuous Glucose Monitoring

Exploratory objective relative to CGM is to compare the effect of each once-weekly 5 mg, 10 mg and 15 mg tirzepatide versus dulaglutide 0.75 mg on daily glucose control and variability measured by CGM at Week 32 for the following endpoints:

- Daily average glucose (mg/dL)
- Duration of time in range < 70 mg/dL (minutes)
- Percentage of time per day in range < 70 mg/dL
- Duration of time in range > 180 mg/dL (minutes)
- Percentage of time per day in range > 180 mg/dL
- Duration of time in range ≥ 70 mg/dL and ≤ 180 mg/dL (minutes)
- Percentage of time per day in range ≥ 70 mg/dL and ≤ 180 mg/dL
- Daily within-day SD (mg/dL)
- Daily mean amplitude of glycemic excursions (MAGE) (mg/dL)

The CGM system will be offered to a subgroup of patients at selected sites in the study [Protocol Addenda I8F-JE-GPGO (1)]. Interstitial glucose (ISIG) values will be collected by the CGM at 15-minute intervals, for a maximum of 96 measurements each day the sensor is worn.

All CGM variables will be derived for each patient and valid CGM day (unless otherwise specified). CGM parameters will then be calculated per visit as the aggregate over CGM days. Continuous glucose monitoring visits will be analyzed under the visit identified in the raw CGM data. All CGM glucose derivations will be calculated in units of mg/dL and then converted to mmol/L, by dividing by 18.

To ensure that CGM outcome variables are only calculated from CGM session days with sufficient data within the period, the following criteria will be used to determine a valid CGM day to be counted in the calculation for a visit (baseline or endpoint):

- Minimum number of measures per day – at least 70% of the total measures that are supposed to be obtained. For example, 70% of 96 measures for the 24-hour period.
- Maximum allowable missing interval – no interval greater than 3 hours between non-missing measures.
- At least 3 days (midnight to next midnight each day) of data during the CGM period, which may require the patient to wear the device for at least 5 days

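### Does the SAP leave it unclear which Week 32 meal tests enter the analysis?

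*SAP*

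**What the plan says.** **Analysis set for the meal test.** SAP 5.5 uses data "using data from all patients who receive at least 1 dose of the investigational product and have evaluable PD parameter". The protocol's section on pharmacodynamic statistical inference (under 4.5.2.2) has the same rule and does not define evaluable either.

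**General populations.** SAP 5.1 states: "Exploratory efficacy parameters will be assessed using the modified intention-to-treat (mITT) population", meaning randomized participants with at least one dose. It continues: "The primary efficacy of tirzepatide versus dulaglutide 0.75 mg at 32 weeks will be guided by the" efficacy estimand, using the EAS. The supplied SAP text does not define the EAS.

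**Status of the endpoints.** Table GPGO.1 in SAP 4.1 has only pharmacokinetic and exploratory objectives. SAP 5.5 opens: "Exploratory objective relative to meal tolerance test is to compare the effect of once-weekly" tirzepatide with dulaglutide.

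**AUC(0-6h).** The abbreviation note to that table reads "area under the concentration versus time curve from time zero to 6 hours after dose". The protocol's objectives table (4.2) has the same note. Attachment 3 of the protocol lists "Dose of investigational product at Week 32" before the meal and no dose at the baseline test.

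**Neighbouring sections.** For continuous glucose monitoring, SAP 5.6 says "the following criteria will be used to determine a valid CGM day to be counted in the calculation for a visit", sets numerical limits and uses on-drug data only. SAP 5.7 censors body composition data after study drug is stopped. SAP 5.5 has no such sentence.

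**The concern.** Three pieces of text seem to pull in different directions on the same visit. The EAS sentence names 32 weeks, which is when the meal test is done, so a reader might think it governs the meal test in place of mITT. Taken literally, the abbreviation note would leave no AUC at Week -1, and the ANCOVA in 5.5 needs that value as its baseline covariate. The word evaluable carries the whole inclusion rule and is not explained, while 5.6 and 5.7 spell their rules out.

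If the texts really conflicted, two analysts could build different data sets for a patient tested after stopping study drug. That would touch the glucose AUC comparison on which the addendum was sized, the other AUC comparisons (5 analytes x 3 doses = 15 in all) and the satiety scale comparisons.

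**Working it through.** **1. Population.** SAP 5.1 puts exploratory efficacy parameters in mITT: randomized, at least one dose. SAP 5.5 calls the meal-test objective exploratory and also asks for at least one dose. Together they give mITT patients who have the parameter. The EAS sentence concerns primary efficacy, and Table GPGO.1 contains none. It therefore has nothing to act on in this addendum and does not displace mITT. No supplied text says that the EAS is restricted to on-drug data, so it cannot be used to infer such a rule for the meal test.

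**2. Time zero.** Protocol 4.1 (footnote b), 4.3.1 and Attachment 3 time the samples from the start of the test meal. Protocol 4.5.2.2.1 calculates the parameters after the meal at both Week -1 and Week 32. Protocol 4.4.2.1 expands AUC(0-6h) as time zero to 6 hours, without mentioning a dose. Only the abbreviation notes mention one. The baseline AUC is well defined.

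**3. Evaluable.** SAP 5.5 specifies a linear-trapezoidal AUC on actual times and an ANCOVA of change with the baseline value as covariate. A patient can enter only if AUC(0-6h) can be computed at both Week -1 and Week 32. That is the natural working meaning of evaluable. It leaves small conventions open: a missing 0- or 360-minute sample, or an unfinished meal.

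**4. Tests after stopping study drug.** Protocol 4.3.1 and Attachment 3 place a dose of investigational product before the Week 32 meal, and the Schedule of Activities shows no meal test at early termination. A Week 32 test done as written is on drug.

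**5. Size, if one off-drug test occurred.** The inputs from SAP 4.2 are 48 patients over 4 arms (12 per arm), SD 250 and difference 330 mg*hr/dL. The plan's statement is "Assuming 1 dropout, the sample size of 11 patients for each treatment group would provide 79% power".

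- Plan's own figure: with 11 per arm, the noncentrality is 330 / (250 x sqrt(2/11)) = 330 / 106.6 = 3.10. The two-sided 5% t-test has 83.8% power (normal approximation 87.2%), not 79%. The t-test gives 79.7% at 10 per arm. The stated power is thus on the low side for the stated inputs. That is a separate matter and does not affect this question.
- Standard error of an arm difference, 12 v 12: 250 x sqrt(1/12 + 1/12) = 102.1.
- One patient excluded, 12 v 11: 250 x sqrt(1/12 + 1/11) = 104.4. The ratio is 104.36 / 102.06 = 1.022, or 2.2% wider.
- One off-drug patient kept: shift = departure / 12. An assumed departure of 100 gives 8.3, 165 gives 13.75 and 330 gives 27.5 mg*hr/dL. The last is 27.5 / 102.06 = 0.27 standard errors.

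The range 0 to 330 is an assumption. The figure 330 is the planned difference between arms, not a limit on what one patient could show. The sample size already treats one patient per arm (1/12 = 8.3%) as having no Week 32 value, so this scenario goes beyond what the plan expects.

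**The case for a change.** The best case for a change is that this sponsor does write such rules when it chooses to. SAP 5.6 requires 70% of readings, no gap over 3 hours and at least 3 days. SAP 5.7 censors after discontinuation. The SAP's version history records that the population for glucose monitoring was clarified in Version 2. The meal test, whose glucose AUC sized the addendum, received nothing similar.

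There is also a computational loose end. AUCs use actual times, and Attachment 3 allows 10 minutes either side at the 360-minute sample. A last sample at 350 minutes leaves 10 minutes unobserved. At an assumed glucose of 100 to 200 mg/dL that is 100 x 1/6 = 17 to 200 x 1/6 = 33 mg*hr/dL for that patient, and no text says whether to extrapolate.

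The facts stand: evaluable is undefined, 5.5 is silent on discontinuation, and a sentence or two would settle both. The inference that the meal-test analysis is therefore unsound does not. The contrast with the other sections has an ordinary explanation. Glucose monitoring is a recording over many days that needs valid-day criteria, and body composition runs to Week 52, where off-drug visits are more likely. The meal test is a single supervised session that includes a dose. The sampling window is the same in every arm and at both tests, so by itself it gives no reason to expect a difference between arms.

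**Conclusion.** The concern does not hold as a conflict, and no change follows. The mITT sentence in SAP 5.1 and the rule in 5.5 agree. The EAS sentence is a stray with no endpoint in this addendum, and the dose wording in the AUC notes is a slip that the procedures correct. Both are clerical. The undefined term is a real but small gap. The AUC method and the ANCOVA already imply most of the definition, and the analysts can fix the remaining conventions before analysis. Protocol 4.5.2 lets analysis changes that do not alter a principal feature be described in the SAP or clinical study report without an amendment. SAP 5.3 already reports study drug disposition by arm, so patients who stopped study drug would be visible.

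Keeping or censoring an off-drug test would each be legitimate, and nothing in the documents shows bias from either. On the illustration above, one patient matters by at most 0.27 standard errors if kept, or 2.2% in standard error if excluded. This rests on three assumptions: the Week 32 test is run as Attachment 3 describes, the departure lies within the assumed 0 to 330 mg*hr/dL, and the main study SAP, which was not supplied and may define the EAS, does not assign the meal test to another set.
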